October 22, 2002— Draft Protocol / Revised 1/26/04 NIDA Treatment Research and Development Division

A Phase 1 Parallel-Group, Double-Blind, Placebo-Controlled Cardiovascular and Behavioral Study Assessing Interactions Between Single Doses of Oral Reserpine and Intravenous Methamphetamine

1. Specific Aims

Reserpine will soon enter clinical trials for methamphetamine dependence. Even if reserpine is an effective pharmacotherapy for methamphetamine dependence, it is likely that addicts will take some illicit methamphetamine during reserpine therapy. Although concurrent use of methamphetamine and reserpine could occur at any time, the likelihood is greatest early in therapy. The pharmacologic effects of reserpine after the first few doses may be different from those after sustained administration. These early pharmacologic effects may be similar to the acute effects of methamphetamine. If the effects of acutely administered reserpine and methamphetamine are similar, additive toxicity could occur. Therefore, it is important to assess acute pharmacologic interactions before exposing patients to reserpine therapy.

In this parallel group clinical pharmacology laboratory experiment, we will assess pharmacodynamic interactions (with a focus on cardiovascular effects) of a 15 mg intravenous methamphetamine dose and single oral doses of reserpine (0.5 and 1.0 mg) or placebo.

The cardiovascular interactions between methamphetamine and reserpine will be assessed using a combination of complementary indices including:

- a) Heart rate (HR), systolic and diastolic blood pressure, and pulse pressure (SBP, DBP and PP) to assess basic cardiovascular function.
- b) Cardiac conductivity and myocyte repolarization assessed with electrocardiogram (ECG) and ECG heart rate corrected QT interval (QTc).
- c) Systemic vascular resistance and cardiac output measured by impedance cardiography (IC).

CNS norepinephrine turnover (using the surrogate measure of urinary MHPG-sulfate excretion) will be used to assess the effects of methamphetamine and reserpine on CNS norepinephrine turnover.

Subjective symptom and mood effects will be measured using Adjective Scales and Visual Analog Scales (VAS) and craving measured by Brief Substance Craving Scale (BSCS).

2. Hypothesis

We predict that a single 0.5 or 1.0 mg oral dose of reserpine given 12 hours before methamphetamine will alter the pharmacological response to methamphetamine by increasing:

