Binding of reserpine to VMAT is probably irreversible, with recovery of sympathetic function dependent on the synthesis of new enzyme and storage vesicles. The cardiovascular and antihypertensive effects of the drug are the best studied. Pharmacodynamic effects begin shortly after the first dose, but it takes several weeks (possibly even months) before maximal effects plateau.

Little human pharmacokinetic data for reserpine are available, probably due to limitations in analytic technologies when the drug was widely used. Because reserpine binds tightly to its site of action and may not be in equilibrium with plasma, it is unlikely that plasma concentrations will be related to pharmacologic effects.

Reserpine undergoes extensive metabolism and none of the drug is excreted unchanged in the urine. However, some reserpine molecules do seem to escape metabolism, since significant amounts of intact reserpine have been found in fecal samples taken from both experimental animals and human beings after either oral or parenteral drug administration (Stitzel 1976). There are no data on the pharmacologic activity of the reserpine metabolites. Orally administered reserpine is readily absorbed from the GI tract. During this process, at least a portion of the drug is metabolized by the intestinal mucosa and then presumably is acted upon by serum esterases. Methylreserpate and trimethoxybenzoic acid are the primary metabolites which result from the hydrolytic cleavage of reserpine. The relative contributions of serum esterases versus hepatic metabolism in the biotransformation of reserpine in vivo are not known.

However, very little unmetabolized reserpine is eventually eliminated in the urine. In the liver, it is quite likely that both microsomal oxidative and hydrolytic enzymes contribute to the metabolism of reserpine.

Reserpine and Amphetamine Interactions

Interactions between amphetamine and reserpine were extensively investigated 50 years ago and helped to define mechanisms of amphetamine effects. Because most of this literature predates Medline, we have summarized the data below. Reserpine acts rapidly. After single doses of reserpine, brain monoamine levels decline within 24 hours and take several weeks to recover (Haggendal and Lindqvist 1964).

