Chronic treatment with reserpine produces a different spectrum of effects than brief (single or only a few doses) treatment with reserpine. In contrast to the reversal of reserpine-induced hypolocomotion by d-amphetamine, rats chronically treated with reserpine are more sensitive to the acute stimulant effects of d-amphetamine. Although chronic reserpine-treated mice show an increased sensitivity to the toxic effects of amphetamine, no increase in lethality was seen (Stolk and Rech 1968). Chronic reserpine and amphetamine seem to produce similar effects with decreased self-stimulation responding in animal models (Leith and Barrett 1980).

Explicit mortality data was not presented in any of the studies described above. However, there were no comments suggesting an increased mortality in animals treated with reserpine and amphetamine (or cocaine).

4. Methods

a. Study Design

This 7-day double-blind, parallel-group, placebo-controlled inpatient study will compare the effects of 15 mg of intravenous methamphetamine given 60 hours before and 12 hours after a single oral dose of reserpine (0.5 or 1.0 mg) or placebo.

Subjects will be randomized to one of three parallel groups. A parallel group design (as opposed to a crossover design) is needed because the duration of action of even a single dose of reserpine is unpredictable. Reserpine irreversibly binds to the vesicular monoamine transporter; reversal of this effect requires synthesis of new transporter, a process that can take from one week to one month.

b. Methods of Data Analysis

As appropriate, statistical group comparisons will be made with PC-SAS's general linear model procedure (SAS Institute Inc., Release 6.04 Edition, Cary, NC, 1990) and with multifactor repeated-measures analysis of variance using SAS (UNIX) or SuperANOVA (Macintosh) software applications. Physiologic data will be transformed to change scores (post-treatment minus pre) and analyzed by repeated measures analysis of variance (ANOVA). After a significant F test, pairwise comparisons will be performed using the least squares means analysis. Effects will be considered statistically significant at P = 0.05.

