We have computed the power of our main measures from a prior methamphetamine study ([name] et al. 1995) similar to the study we propose. In this study, 30 mg of intravenous methamphetamine was administered and changes in heart rate $(20\pm17; mean\pm SD)$ were the smallest differences between active drug and placebo conditions. Based on Cohen's (1988) effect size formula, data from a study with a sample size of 6 would yield a power of 0.80. However, because the parallel group design increases between-subject variance, a larger n is needed. Therefore, correcting for the slightly small effect size, we estimate that a sample size of 10 per group will be sufficient to achieve a power of .80, using a two-tailed alpha = 0.05.

c. Subject Selection

1) Who and Why

Methamphetamine-experienced subjects between the ages of 21 and 45 years, in good physical and mental health, with no cardiovascular pathology will be accepted into the study.

2) Total Number — 30 Subjects

3) Inclusion/Exclusion Criteria

Inclusion Criteria

Subjects will be included in the study if they:

- 1) Are normotensive and between the ages of 21 to 45.
- 2) Are in good physical and mental health and have a body mass index between 18 and 30.
- 3) If female and have childbearing potential, are using an acceptable method of contraception and are not pregnant.
- 4) Are able to give voluntary informed consent.

Exclusion Criteria

Subjects will be excluded if:

- 1) They are currently dependent (using DSM–IV criteria) on alcohol or other psychoactive drugs (except nicotine and caffeine).
- 2) They have positive qualitative urine screens for drugs of abuse on admission the morning of dosing or during the screening examinations.
- 3) They have significant medical or psychiatric illnesses that might impair their ability to safely complete the study, that might be complicated by study medication, or that may interfere with absorption, distribution, metabolism or excretion of drugs.
- 4) They have a history of major depression or pharmacotherapy for depression or anxiety within the last year.

Subjects will not be allowed to take concomitant medications (other than birth control pills), whether prescription or over-the-counter (OTC); subjects needing regular doses of prescription medications will be excluded.

d. Subject Recruitment

1) Sources and 2) Initial Contact Method

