Physiological Monitoring. On the days without methamphetamine challenges (days 0, 2, 3, and 5), subjects will have vital signs (heart rate, standing and supine blood pressure, respiratory rate, oxygen saturation, core temperature, and weight) and the noninvasive cardiac profile determined daily at 10 AM, 4 PM, and 8 PM. Vital signs will be obtained using a Critikon or Escort II monitor or a similar bedside device and noninvasive cardiovascular parameters measured using the instruments described above. On the days methamphetamine challenges are performed (study days 1 and 4), vital signs and the noninvasive cardiac profile will be obtained 15 minutes before and 5, 15, 30 and 60 minutes and at 1, 2, 3, 4, 6, 8 12, 18, 24, 30 36 and 48 hours after the infusion.

Subjective Measures. Subjective measures will be obtained daily at 8 AM, 4 PM, and 8 PM on study days 0, 2, 3 and 5. On days 1 and 4, when methamphetamine is administered, measures will be obtained starting 15 minutes before, and at 5, 15, 30, and 60 minutes, and 1, 2, 3, 4, 6, 8 12, 18, 24, 30 36, and 48 hours after the infusion. Items will include "any drug effect," "good drug effect," "bad drug effect," "headache," "dizziness," "desire for methamphetamine," and "craving for methamphetamine." The Beck Depression Inventory (Beck et al. 1996) will be administered daily at 4 PM.

Biosample Measures. All urine will be collected in 24-hour intervals and assayed for MHPG-sulfate by HPLC. On days 1, 4, and 6, aliquots will be sent for qualitative drugs of abuse screens.

Cardiovascular Measures. A series of non-invasive complementary cardiovascular measures assessing ventricular function (impedance cardiography), cardiac conductance and repolarization (ECG QTC interval), and peripheral vascular dynamics (impedance cardiography) will be obtained frequently throughout hospitalization. Data acquisition for the entire non-invasive panel requires about 10 minutes.

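### Section 4.b leaves undefined the 'pre' value in its change scores and the role of the day-1 response; the readings estimate different quantities, can miss an additive rise, and lose precision

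*Protocol*

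**What the plan says.** The hypothesis in section 2 is that reserpine "will alter the pharmacological response to methamphetamine by increasing" several measures, heart rate and blood pressure among them. Section 4.a says the study "will compare the effects of 15 mg of intravenous methamphetamine given 60 hours before and 12 hours after a single oral dose of reserpine" or placebo, in three parallel groups.

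For the analysis, section 4.b says "Physiologic data will be transformed to change scores (post-treatment minus pre) and analyzed by repeated measures analysis of variance (ANOVA"). It names a general linear model procedure and analyses "with multifactor repeated-measures analysis of variance using SAS (UNIX) or SuperANOVA (Macintosh) software applications". It does not list the factors, define 'pre', or state what the first challenge contributes to the comparison of groups.

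The schedule is in section 4.f. Under Physiological Monitoring it reads "On the days methamphetamine challenges are performed (study days 1 and 4"), and vital signs and the cardiac profile "will be obtained 15 minutes before and 5, 15, 30 and 60 minutes", then at intervals to 48 hours. Reserpine is given at about 10 PM, 12 hours before the second infusion. Section 3 says of reserpine: "Pharmacodynamic effects begin shortly after the first dose".

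**The concern.** At the second challenge, the scheduled reading between reserpine and the infusion is the one 15 minutes before the infusion. It is therefore taken after the randomised treatment, at a time when the protocol expects that treatment to be acting. Whether 'pre' means this reading or one taken before reserpine decides whether reserpine's own resting effect is subtracted out or left in. Section 4.b does not choose.

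The choice matters for the purpose of the trial. Section 1 worries that if the two drugs act alike, their toxicity may add. Effects that simply add raise the absolute level reached without changing the increment due to methamphetamine. An analysis confined to the day-4 increment would then report no difference between groups.

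A second matter is efficiency. Every subject who reaches day 4 also has a methamphetamine response recorded before reserpine. With 10 per group, how that response is used has a material effect on power.

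**Working it through.** **1. What each reading estimates.** Let μ be the resting level, m the methamphetamine effect under placebo, b the reserpine effect on the resting level, and g the additive interaction. The expected day-4 values are:

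- Placebo: pre-infusion μ, post-infusion μ + m.
- Reserpine: pre-infusion μ + b, post-infusion μ + b + m + g.

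The contrasts, reserpine minus placebo, are:

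- Change from the day-4 pre-infusion value: (m + g) − m = g.
- Day-4 change minus day-1 change: also g, since day 1 precedes reserpine in all groups.
- Change from a pre-reserpine value: (b + m + g) − m = b + g.
- Absolute post-infusion level: b + g.

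The protocol gives no size for b at 12 hours, so the values below are illustrations. A simulation agreed with the algebra to within 0.1 unit.

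| b | g | Day-4 change | Change from pre-reserpine value |
|---|---|---|---|
| −10 | 0 | 0 | −10 |
| −10 | 10 | 10 | 0 |
| 5 | 0 | 0 | 5 |
| 5 | 10 | 10 | 15 |

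The third row is the purely additive case: the level reached is 5 higher and the day-4 change shows nothing. The second row shows the converse: a baseline taken before reserpine conceals a real interaction of 10.

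**2. The plan's own power figure.** Section 4.b reports that in a prior 30 mg methamphetamine study "changes in heart rate $(20\pm17; mean\pm SD)$ were the smallest differences between active drug and placebo conditions". The standardised effect is 20/17 = 1.176. The one-sample (paired) normal formula gives n = (1.960 + 0.842)²/1.176² = 5.67, so 6, which matches the protocol's figure of 6 for power 0.80. For a pairwise comparison with 10 per group, the noncentrality is 20/(17 × √(2/10)) = 2.631. A two-sided 0.05 t test on 27 df (30 subjects less 3 groups) then has power 0.72, not the stated 0.80.

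**3. Precision by use of day 1.** Let ρ be the correlation between a subject's day-1 and day-4 changes. The protocol gives none, so ρ is an assumption.

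- Day 1 ignored: SD 17, 27 df.
- ANCOVA on the day-1 change: SD 17√(1 − ρ²), 26 df.
- Session difference (day-4 change minus day-1 change): SD 17√(2(1 − ρ)), 27 df.

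| ρ | Unadjusted power | ANCOVA SD | ANCOVA power | Session-difference SD | Session-difference power |
|---|---|---|---|---|---|
| 0.3 | 0.72 | 16.2 | 0.76 | 20.1 | 0.57 |
| 0.5 | 0.72 | 14.7 | 0.83 | 17.0 | 0.72 |
| 0.6 | 0.72 | 13.6 | 0.89 | 15.2 | 0.81 |

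The variance factors differ by 2(1 − ρ) − (1 − ρ²) = (1 − ρ)², which is positive for any ρ below 1, so ANCOVA always has the smaller residual variance. The session difference does worse than ignoring day 1 when ρ < 0.5.

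**The case against.** The strongest objection is that the day-4 change score is the right contrast for the stated hypothesis. Section 2 concerns the response to methamphetamine, and subtracting a reading taken under reserpine removes reserpine's resting effect, leaving g. This stands. A reader might infer that the contrast is biased by the resting effect, because a fall at rest with an unchanged post-infusion level would show up as potentiation. But in that case methamphetamine has raised the value by more than it did under placebo, which is a genuine interaction on the additive scale. The documents do not support calling that result spurious.

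A reader might also infer that the day-1 response is discarded. That goes beyond the text. Section 4.a announces a before-and-after comparison, and a multifactor repeated-measures model can hold session as a factor. What stands is narrower: section 4.b does not say so, and if session is a factor, the group-by-session contrast is the session difference, which is less precise than covariate adjustment.

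It can also be said that factors and covariates belong in a statistical analysis plan, which may exist and is not shown, and that absolute values are recorded and could be reported. Both are fair. However, the protocol has already fixed the change-score transformation and the repeated-measures ANOVA, and those choices carry the consequences above. Finally, preferring ANCOVA is a question of efficiency, not of validity, and the gain depends on a correlation the protocol does not give.

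**Conclusion.** The point holds as an ambiguity and a missed improvement. Section 4.b admits readings that estimate g or b + g, and these can lead to different conclusions about safety. The day-4 change is valid for g but cannot show a purely additive rise in absolute heart rate or blood pressure, which is the concern in section 1.

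On precision, ANCOVA on the day-1 response raises power from 0.72 to between 0.76 and 0.89 for ρ from 0.3 to 0.6. A session difference gives 0.57 to 0.81 over the same range. These figures rest on the assumed correlations, and on the protocol's 20 ± 17 taken as a benchmark. That input is a methamphetamine-versus-placebo effect at 30 mg, not a reserpine interaction at 15 mg, so the comparison between methods is more secure than the absolute power. Additivity is also assumed; a ceiling or reflex effect could tie response to resting level, and the protocol gives no figure for that.

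**What to change.** In section 4.b:

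- Define 'pre' as the pre-infusion reading of the same session.
- Keep the day-4 change from pre-infusion as the interaction analysis. Fit it by ANCOVA or a mixed model with treatment group as a factor and the same subject's day-1 change at the matching time as a covariate.
- Alongside it, analyse the absolute day-4 post-infusion levels, at peak and by time, adjusted for the day-1 values. State that this estimates b + g. It complements the response contrast and does not replace it.
- Report the reserpine effect on the day-4 resting value as a separate result, so that the other two can be read together.

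The readings needed are already scheduled on both challenge days. The cost is analysis wording and one or two degrees of freedom.

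### The power of .80 claimed for 10 per group does not follow from the stated inputs, which give about 0.70, and the effect assumed is methamphetamine versus placebo, not reserpine versus placebo

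*Protocol*

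**What the plan says.** The power paragraph in section 4.b (Methods of Data Analysis) starts from a prior study: "In this study, 30 mg of intravenous methamphetamine was administered". Heart-rate changes in that study, 20 ± 17 (mean ± SD), "were the smallest differences between active drug and placebo conditions". From this the protocol concludes that "data from a study with a sample size of 6 would yield a power of 0.80". It then says that "because the parallel group design increases between-subject variance, a larger n is needed", adds a correction for a somewhat small effect size, and ends with: "we estimate that a sample size of 10 per group will be sufficient to achieve a power of .80", "using a two-tailed alpha = 0.05". It gives no value for the inflated variance or the reduced effect.

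Earlier in the same section the analysis is set out as repeated-measures ANOVA on change scores. "After a significant F test, pairwise comparisons will be performed using the least squares means analysis".

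Section 4.f (Drug Doses and Conditions) assigns 10 subjects to each of reserpine 0.5 mg, reserpine 1.0 mg and placebo for reserpine. All three groups receive 15 mg methamphetamine before and after that dose.

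**The concern.** There are two separate faults.

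- **Arithmetic.** A two-group comparison with d = 1.18 and 10 per group does not have 80% power at two-sided 0.05.
- **Comparison.** The effect size belongs to methamphetamine against placebo at 30 mg. This trial has no methamphetamine-placebo group. Its between-group question is how far reserpine changes the response to 15 mg methamphetamine, and the protocol assumes no size for that change. Using 20 bpm amounts to supposing that reserpine adds as much again as the whole effect of twice this trial's methamphetamine dose.

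What is at stake is how a non-significant result can be read. Section 3 gives safe use alongside methamphetamine as one reason for the study, and section 2 predicts no alteration of several measures. A claimed power of .80 makes a null result look more informative than the sample size supports.

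**Working it through.** **Inputs, all from the protocol.** Difference 20 bpm, SD 17, two-sided alpha 0.05 and n = 10 per group in three groups (sections 4.b and 4.f). d = 20/17 = 1.176.

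**The n = 6 step.** The one-sample normal formula gives n = (1.96 + 0.84)²/d² = 5.67, rounded up to 6 (power 0.82). The paired t-test at n = 6 gives 0.64 two-sided and 0.79 one-sided. So 6 is a within-subject figure. It can arise from the normal approximation or from a one-sided t-test, and the protocol does not say which.

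**The step to 10 per group.** For two groups the noncentrality is d√(n/2) = 1.176 × √5 = 2.63.

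| Method, 10 per group | Power |
|---|---|
| Two-sample t, two-sided, 18 df | 0.70 |
| Same contrast, pooled ANOVA error, 27 df | 0.72 |
| Normal approximation, two-sided | 0.75 |
| Two-sample t, one-sided | 0.81 |

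The two-sample normal formula, n = 2(1.96 + 0.84)²/d², gives 11.3, so 12 per group. By the t-test, 12 per group gives 0.79 and 13 gives 0.82.

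**The stated adjustments.** A larger variance or a smaller effect lowers d, so neither can raise 0.70 to 0.80. Reaching 0.80 with 10 per group and 20 bpm needs an SD of about 15.1 (20/1.325), which is below 17.

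**What 10 per group can detect.** The t-test has 80% power at d = 1.325, and 1.325 × 17 = 22.5 bpm. At SD 17, power for smaller differences (chosen for illustration) is:

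| Difference | Power |
|---|---|
| 20 bpm | 0.70 |
| 15 bpm | 0.46 |
| 10 bpm | 0.24 |

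**The F-test gate.** These are simulated probabilities that both the three-group F and the 1.0 mg versus placebo contrast (27 df) are significant. Without the gate the contrast has power 0.72. The protocol gives no pattern of means, so all three patterns are assumptions.

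| Means for placebo, 0.5 mg, 1.0 mg (bpm) | Both significant |
|---|---|
| 0, 10, 20 | 0.58 |
| 0, 20, 20 | 0.65 |
| 0, 0, 20 | 0.65 |

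**The case against.** **Sidedness.** A one-sided t-test comes close to both stated figures: 0.79 at n = 6 and 0.81 at 10 per group. Several hypotheses in section 2 are directional. A reader might infer that n = 6 can come only from the normal approximation, but these figures rule that out. A mislabelled one-sided calculation is a plausible source. The text nevertheless says two-tailed for the 10 per group, and on that basis .80 is wrong.

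**The planned model.** Every subject is challenged before and after reserpine or placebo, so the first response could serve as a baseline. An effective SD of 15.1 would follow from SD 17 with a between-session correlation of about 0.46 under covariate adjustment (17√(1 − ρ²)), or about 0.61 for a difference of responses (17√(2(1 − ρ))). This stands as a limit on the finding: 0.70 is for a single change-score comparison. But the protocol gives no correlation and claims no such gain.

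**Meaning of the 17.** If it is the SD of a within-subject drug-minus-placebo difference, the between-group SD is 17/√(2(1 − ρ)). That is 15.1 or less only if ρ is about 0.37 or less. Such a fall in SD would contradict the protocol's statement that the parallel design increases variance.

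**Other contrasts.** Both reserpine groups combined against placebo (20 versus 10) would have power 0.83, but that is not the planned comparison.

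**Consequence.** A reader might infer that a non-significant test would be taken as proof of safety. No section sets such a rule. Section 3 also describes the aim as exploratory, and section 4.f protects subjects through individual criteria.

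**Conclusion.** The power statement is wrong as written. On the protocol's own 20 ± 17, 10 per group and two-tailed 0.05, power is about 0.70, and no standard two-sided comparison of two groups of 10 gives more than 0.75. Separately, even a correct figure would describe 30 mg methamphetamine against placebo and not the comparison this trial makes.

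The 0.70 assumes an SD of 17 in each group and one change score per subject. It is not shown to be the power of the full repeated-measures analysis, so the documents do not support saying that the planned model cannot reach 0.80. What they show is that .80 does not follow from the inputs given. Nor should 0.58 be quoted alone as the gated power: it belongs to one assumed dose pattern, and the range over the three tried is 0.58 to 0.65. Finally, 13 per group would give 0.82 for a 20 bpm difference, but no reserpine effect of that size has been justified, so the finding is not in itself a case for enlarging the trial.

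**What to change.** Keep 30 subjects and replace the .80 claim in section 4.b with wording such as:

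> With 10 per group and two-sided 0.05, a single change-score comparison of a reserpine group with placebo has 80% power for a difference of about 22.5 bpm if the SD is 17. Power is about 0.70 for 20 bpm, 0.46 for 15 bpm and 0.24 for 10 bpm, before the F-test gate. Both the 20 bpm and the SD of 17 come from 30 mg methamphetamine versus placebo in a prior study; 20 bpm is a reference value, not an expected reserpine effect.

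The last sentence matters. Without it, 20 bpm would simply be relabelled as a reserpine effect with its origin hidden.

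Remove the n = 6 figure as support for 10 per group, or state the test and sidedness behind it (paired t: 0.64 two-sided, 0.79 one-sided).

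The cost is one rewritten paragraph and a less favourable stated power. Design, analysis and number of subjects do not change.

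### Only one pre-infusion set is scheduled per challenge; if it is the baseline for the change scores, precision is lost that replicate baselines would cheaply recover.

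*Protocol*

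**What the plan says.** Protocol section 4.f.1 (Physiological Monitoring) sets the readings for the two challenge days: "vital signs and the noninvasive cardiac profile will be obtained 15 minutes before and 5, 15, 30 and 60 minutes". A list of hourly and later times follows, the last of them at 48 hours. The 60-minute and 1-hour entries are the same time, so each session has one pre-infusion set and 15 distinct post-infusion times. On the other days the same section has "the noninvasive cardiac profile determined daily at 10 AM, 4 PM, and 8 PM", but gives those readings no role as a baseline.

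Protocol section 4.b (Methods of Data Analysis) states: "Physiologic data will be transformed to change scores (post-treatment minus pre) and analyzed by repeated measures analysis of variance (ANOVA"). For the group comparisons that come next, its rule is: "After a significant F test, pairwise comparisons will be performed using the least squares means analysis". It does not say which reading or readings make up *pre*, does not mention replicates or a baseline covariate, and does not name the F test (group, or group by time) that opens the pairwise comparisons.

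The only variance figure is in the power paragraph of 4.b, from a prior 30 mg study: "changes in heart rate $(20\pm17; mean\pm SD)$ were the smallest differences between active drug and placebo conditions".

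**The concern.** Suppose *pre* is the set taken 15 minutes before the infusion. One reading is then subtracted from all 15 post-infusion values of its session, and its error moves the subject's whole change profile up or down together. Averaging over post-infusion times shrinks the post-infusion noise but leaves this shift untouched. The shift adds to the between-subject variance of heart rate, blood pressure, cardiac output and vascular resistance changes, with only 10 subjects per group. A comparison of the two challenges in which each uses its own baseline carries two such errors.

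An analysis plan can define *pre* or add a covariate later, but it cannot recover replicate readings at the time of infusion that were never scheduled. The number of pre-infusion sets therefore has to be settled in the protocol.

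**Working it through.** **Inputs.** From the protocol: 1 pre-infusion set and 15 distinct post-infusion times (4.f.1); 10 per group, two-tailed 0.05, heart-rate change 20 ± 17 bpm (4.b). Assumed: equal noise SD σ per reading, with σ = 4, 6 or 8 bpm; pre-infusion error independent of post-infusion errors; and the SD of 17 as the SD of a single-time change that already contains one single-reading baseline error.

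**The protocol's own figure.** With d = 20/17 = 1.176, the one-sample normal formula gives ((1.960 + 0.842)/1.176)² = 5.67, which rounds up to the protocol's 6. For two groups of 10, the noncentral t with 18 df and noncentrality 1.176 × √(10/2) = 2.63 gives power 0.70 (0.75 by the normal approximation), not the stated 0.80. That shortfall is a separate matter; 0.70 is only the starting value here.

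**Baseline share of measurement error.** For the mean of k post values minus the mean of m pre values, with correlation ρ among post-infusion errors:

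error variance = σ² × [1/m + (1 + (k − 1)ρ)/k]

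With m = 1 and k = 15 the baseline share is 1/[1 + (1 + 14ρ)/15]:

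| ρ | post-infusion term | baseline share |
|---|---|---|
| 0 | 0.067 | 94% |
| 0.2 | 0.253 | 80% |
| 0.5 | 0.533 | 65% |
| 0.8 | 0.813 | 55% |

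- Single post-infusion time (k = 1): 1/(1 + 1) = 50%.
- Group-by-time contrasts: 0%. The shared baseline cancels from any difference between two times; in a simulated data set, change scores and raw post values gave the same within-subject deviations to rounding error.

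With ρ = 0, three pre-readings instead of one cut the time-averaged error variance from 1.067σ² to 0.400σ² (62.5% lower). At a single time the cut is from 2.00σ² to 1.33σ².

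**Power at a single time, 20 bpm, 10 per group.** Averaging three independent pre-readings replaces σ² by σ²/3, so the total variance becomes 289 − (2/3)σ². If the pre-reading errors correlate 0.5, their mean has variance σ²(1 + 2 × 0.5)/3 = (2/3)σ², and the total becomes 289 − (1/3)σ².

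| σ (assumed) | SD, independent | variance cut | power | SD, correlation 0.5 | power |
|---|---|---|---|---|---|
| one pre-reading | 17.00 | – | 0.701 | 17.00 | 0.701 |
| 4 | 16.68 | 4% | 0.718 | 16.84 | 0.709 |
| 6 | 16.28 | 8% | 0.738 | 16.64 | 0.720 |
| 8 | 15.70 | 15% | 0.769 | 16.36 | 0.734 |

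**Power for the 15-time average, all errors independent.** The variance is 289 − 2σ² + σ²(1/m + 1/15), which also assumes that a subject's true response is the same at all times. Going from one to three pre-readings moves power from 0.724 to 0.741 (σ = 4), 0.754 to 0.794 (σ = 6) and 0.798 to 0.872 (σ = 8). This is the favourable case.

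**The case against.** A reader might infer that every physiologic change score hangs on one reading, and that its noise is the dominant error in the group comparison. The documents do not support that.

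- The 94% share needs an average over all 15 times to 48 hours and independent errors. The share is 55% to 80% with correlated post-infusion errors, half at one time and nil for group by time. Section 4.b does not name the deciding F test or an averaging window.
- Section 4.b says only *pre*. Sets on day 0 precede the first challenge and sets on day 3 precede the reserpine dose, so an analysis plan could build a baseline from several readings. Those sets are not taken just before an infusion, so they do not fully replace replicates, but the dependence on one reading is conditional.
- No per-reading SD is given, nor the number of baseline readings in the prior study. If that study averaged several, subtracting (2/3)σ² from 289 is wrong. The 20 bpm is methamphetamine against placebo at 30 mg, not a difference between reserpine groups after 15 mg. The power figures are therefore illustrations.
- The single-time gain is small and reaches 0.80 in none of the cases shown. Readings 15 minutes apart share the subject's state, so the correlated case deserves at least equal weight. At σ = 8, reading error would be 2 × 64 = 128 of 289, or 44% of the change variance, which is a lot.

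All four points stand as limits on size and wording. They do not touch the schedule itself: one pre-infusion set per challenge, and no replicate that could be averaged later.

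**Conclusion.** The point holds as a modest loss of precision. It is neither an error nor a contradiction in the plan, and the randomised comparison is not biased. If *pre* is the set 15 minutes before the infusion, its error is the largest measurement-error component in a time-averaged group comparison. It is not larger than the post-infusion error at a single time and plays no part in group-by-time contrasts.

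These shares concern measurement error only, not total variance. On the assumptions above, the baseline reading's share of total single-time variance is σ²/289, or 6%, 12% and 22% for σ = 4, 6 and 8. Real differences between subjects may well weigh more. The single-time gain from three pre-readings is 0.01 to 0.07 in power across the cases shown. It is worth taking because it costs little and must be arranged before data collection.

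**What to change.** In 4.f.1, schedule three pre-infusion sets in the same posture in both challenge sessions, for example 45, 30 and 15 minutes before the infusion. In 4.b, define *pre* as the mean of the three sets of that session, and include that baseline as a covariate in the general linear model already named there. The covariate needs no new data and would help even if the schedule stayed as it is.

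The cost is two more non-invasive sets per session, at about 10 minutes each by the protocol's own estimate and on equipment already in use, plus a sentence or two in 4.b. The downside is about 30 more minutes of monitoring before each infusion.
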